The project relies on PPI involvement at all stages. PPI representatives from our core project team ([name]), our project-specific PPI group and charity collaborators (Equally Well at The Centre for Mental Health) will be consulted approximately every four months (more frequently if required) and involved in coproduction activities as research progresses. Complexities in this area, which include the heavy tobacco addiction experienced by many mental health service users, call for an approach that supports maximal service user orientation for the development of a relevant, acceptable and successful intervention. PPI representatives will be involved in the planning of the research, the development of service user-oriented intervention and research materials (e.g. leaflet), aspects of research conduct (e.g. development of topic guides for qualitative interviews in the pilot trial), networking with existing PPI groups nationally, and dissemination activities with a focus on informing national policy in this area.

STUDY FLOW CHART

Patient mental health records will be screened by research fellows prior to visits to CMHT or GP sites for CPA review/physical health screen. On appointment day, MHR or trained CPN will check eligibility and consent participants at community clinic/GP.

Inclusion criteria

[figure not shown]
 Participants who are current smokers, interested in cutting down or quitting; 2. No mental health inpatient stay in last 3 months; 3. Age ≥ 18 years; 4. Proficient in English or Urdu; 5. Capacity to provide consent

Exclusion criteria

 Current use of e-cigarettes;
 Participation in other smoking cessation trial within last 6 months;
 Pregnant or breastfeeding;
 No treatment for comorbid drug or alcohol problems in last 6 months;
 Alzheimer's disease or dementia diagnosis

Consented eligible participants

Baseline assessment (on site): sociodemographic/smoking behaviour characteristics, health behaviours, primary mental health diagnosis (if available), mental health history

^{*}From enrolment or target quit date (whichever is later; participants are given a week's grace period to set their quit date), carried out at community/GP dinks or at participant home; CMHT – Community Mental Health Team; GP – General Practitioner; CPA – Care Programme Approach; MHR – Mental Health Researcher; CPN – Community Psychiatry Nurse

ABREVIATIONS

Abbreviation Expansion

AE Adverse Event

BCT Behaviour Change Technique

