At a scheduled appointment with a clinician, a brief consultation will be conducted with participants to provide necessary instructions for use of the kit. This appointment can be an online if this is usual practice for those on the online pathway. All participants will be encouraged to consider quitting and to set a target quit date within a week. As set quit dates are likely to vary widely and may change over time, all participants will have a two week 'grace period' from enrolment to decide whether they chose to set a target quit date or not. Participants will be asked to start using the e-cigarette when they quit and to seek out local vape shops to obtain further e-liquid, suited to their individual needs and flavour preference. Participants who do not wish to set a target quit date will be encouraged to use the e-cigarette to reduce cigarette consumption as soon as possible.

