3.5 Randomisation and allocation concealment

The intervention allocation will be determined by block computer-randomisation to ensure that each trial site has an equal proportion of intervention and control group participants. Those on the online pathway (pathway 1; see 3.6.3) will be informed electronically via email and those on the paper-based pathway (pathway 2; see 3.6.3) will

open a sealed envelope at their appointment. Randomisation will occur after consent to take part in the study has been obtained. Due to the nature of the intervention, it will not be possible to blind participants or all researchers to treatment allocation. The lead applicants, co-applicants, and statisticians, however, will be blinded.

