3.6.2. Recruitment

Each Trust will be allocated a part-time dedicated MHR to support project delivery in the respective localities. Patients with an appointment planned in the coming weeks will be invited to part by letter, which will be sent from the patient's mental health team, or GP surgery for primary care patients. A follow-up call or text will be sent after 7 days.

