Eligible, consented participants will be asked to complete a brief baseline questionnaire, which will be administered via GDPR-compliant online survey tool REDcap (or in person at the same scheduled appointment as consent, which will require the participant to attend their appointment 30 minutes early to meet with the CSO) assessing sociodemographic and smoking behaviour characteristics, with mental health diagnosis and history being obtained from health care records. For those following the online pathway, once a participant has completed and returned the baseline assessment materials, a link will be sent to the participant to inform them of which group they have been randomised to. For those on the paper-based pathway this will be done in person via a sealed envelope (randomisation will have been generated prior to this by computerised block randomisation at the UCL Clinical Trials Unit see 3.4). At this stage, interaction with participants allocated to the control group will stop to allow them to attend their appointment and receive care as usual. Participants allocated to the intervention group will also attend their appointment and receive care as usual but in addition will receive the e-cigarette starter kit, a leaflet and brief explanation (see 3.5.1).

Follow-up of participants at 1 month in phase 1, and at 1 and 6 months in phase 2, will be undertaken by dedicated mental health researchers. Follow-up surveys will be completed via telephone with an option to receive this by post if preferred. In-person follow up at CMHT sites or participants' homes will be required to biochemically validate self-reported abstinence only through carbon monoxide readings (likely to affect approximately 12 participants in phase 1, and 94 participants in phase 2 as per expected abstinence in control and intervention arms in both the feasibility and full trial; see subsections 3.9 and 4.6 of the submitted application). Figure 1 shows a flow diagram of the participant journey through the study. For COVID-19 risk management, social distancing and hygiene measures will be strictly observed and the study team and participants briefed in advance of the follow up visit. Individual mouth pieces for the monitors will be discarded immediately after use and the monitor core piece disinfected. Staff and participants will be provided with PPE – surgical face masks and plastic gloves.

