3.6.4 Procedural variations

During Phase I, we will also pilot two procedural variations at selected sites to determine the scalability of the intervention for Phase II. First, to account for the overrepresentation of some ethnic minorities in the study population, materials (including leaflets, questionnaires, participant information sheets etc.) will be available in both English and Urdu and the intervention delivered by a bilingual MHR at specific sites to allow PWMI with limited English to participate in the study.

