The acceptability of the intervention and research procedures will be investigated using a short proforma based on the Theoretical Framework of Intervention Acceptability [63], provided to all participants at follow-up. This will be complemented by qualitative interviews conducted with a sample of approximately 18 participants from the intervention and control group (including, wherever possible, those who disengaged during the course of the study). We will gain insights into patients' experience with the intervention and barriers to and facilitators of success, both in terms of the intervention content and the research process. MHR (or CPN) delivering the intervention in each Trust will provide detailed feedback on their experience, and on barriers and facilitators to

delivery, through feedback diaries and interviews; in addition, in-depth qualitative interviews will be conducted with six MHR/CPNs (two from each Trust).

The attrition rate will be measured as the number of participants who fail to complete follow-up at 1 month. In order to ensure a sufficiently robust effect estimate, which can be affected by high attrition rates in intention to treat analyses [64], attrition rates should not exceed 30%, typical for smoking cessation trials in this population [65] (see 3.14). Reasons for withdrawal will be obtained, where possible. In addition, adherence to treatment (e-cigarette use) will be assessed at 1-month follow up.

3.8.2.2 Clinical (smoking-related) outcomes: This is the primary clinical outcome measure for the feasibility trial, assessed at 1-month follow up. Continuous abstinence will be defined as not having smoked in the two weeks prior to follow-up (weeks 5 and 6 from enrolment), verified by a CO reading below 10 ppm, in keeping with the standard measure used in Stop Smoking Services. This measure will be used to determine whether to progress to Phase II and a full trial, based on the confidence interval approach (see 3.9 and 3.14).

3.8.3 Secondary outcome measures:

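### The protocol permits, and its staffing makes likely, that unblinded researchers who recruited or treated a participant also collect that participant's abstinence outcome, with no safeguard for the self-report or the effort to obtain CO readings

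*Protocol*

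**What the plan says.** Follow-up at 1 month in Phase I, and "at 1 and 6 months in phase 2, will be undertaken by dedicated mental health researchers" (Protocol 3.6.3). Section 4.3 carries the Phase I procedures into Phase II.

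The mental health researcher (MHR) has other duties as well:

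- Staffing (3.6.2): "Each Trust will be allocated a part-time dedicated MHR to support project delivery in the respective localities".
- Eligibility and consent (study flow chart): "On appointment day, MHR or trained CPN will check eligibility and consent participants at community clinic/GP".
- Delivery (3.8.2.1): "MHR (or CPN) delivering the intervention in each Trust will provide detailed feedback on their experience"; and, as a Phase I variation (3.6.4), "the intervention delivered by a bilingual MHR at specific sites".
- Delivery, described differently (3.4.1): "At a scheduled appointment with a clinician, a brief consultation will be conducted with participants to provide necessary instructions for use of the kit".

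On blinding, 3.5 states that "it will not be possible to blind participants or all researchers to treatment allocation", and then: "The lead applicants, co-applicants, and statisticians, however, will be blinded". Section 4.7.1 adds only that the analysing statistician is blinded.

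The follow-up survey is by telephone, with post as an option, and an in-person CO reading is taken only from those who report abstinence (3.6.3). The primary outcome needs both self-reported 7-day abstinence and CO below 10 ppm at 6 months (4.5.1). Participants lost to follow-up count as smokers (4.7.1).

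**The concern.** The primary outcome begins with an answer given to a caller. If the caller knows the arm, or supplied and explained the device, two things can differ between arms without anyone intending it: how the abstinence question is put and answered, and how hard staff work to reach the participant and complete a CO visit. The second needs no false report. A true quitter without a CO reading cannot be counted as a success, so unequal effort shifts the primary outcome directly.

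The likely direction favours the intervention. Section 3.6.3 ends research contact with controls at allocation, apart from follow-up, while the intervention arm goes on to receive a kit and a consultation. Also exposed are the 1-month abstinence outcome behind progression criterion (b) in 3.13 and the purely self-reported secondary outcomes, such as cigarettes per day and quit attempts, which have no CO check.

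**Working it through.** **1. Roles set side by side.** MHRs undertake follow-up (3.6.3). An MHR or community psychiatric nurse (CPN) checks eligibility and takes consent (flow chart), and an MHR or CPN delivers (3.8.2.1; a bilingual MHR in 3.6.4). Each Trust has one part-time MHR (3.6.2). No section names a separate or masked assessor or bars an MHR from following up his or her own participants. Overlap is therefore permitted, and with one MHR per Trust it is the likely default.

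**2. Would a different caller stay masked?** Not with the present content and no set question order. Follow-up asks about e-cigarette adherence (3.8.2.1), gives controls a usual-care proforma (3.8.3.1) and, at 6 months, records continued use in one arm and new use in the other (4.5.2.3). If such items come first, the caller learns the arm before asking about abstinence.

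**3. The plan's own figure.** Inputs from 4.6: 7.7% against 14.4%, 370 per group, two-sided 0.05. Exact power of Fisher's test (the first test in 4.7.1) is 80.4%, matching the stated 80%. A continuity-corrected sample size formula gives 372 per group, close to the stated 370. The sample size is not in question.

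**4. How few people matter.** Expected quitters are 370 × 0.077 ≈ 28 and 370 × 0.144 ≈ 53. With 28 in the control arm, Fisher's test first reaches significance at 45 in the intervention arm, 17 more.

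**5. Illustration.** Let e be the share of intervention-arm non-abstainers who wrongly claim abstinence and also pass CO, with none in the control arm. The documents give no value, so e is assumed. Under no true effect at 7.7%, the observed intervention rate is

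0.077 + (1 − 0.077) × e = 0.077 + 0.923e,

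and the extra false quitters number 370 × 0.923e. The last column is the exact probability of a significant Fisher result favouring the intervention, 370 per arm.

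| e (assumed) | Observed rate | Extra quitters | False result for intervention |
|---|---|---|---|
| 0 | 7.7% | 0 | 1.8% |
| 0.5% | 8.2% | 1.7 | 3.2% |
| 1% | 8.6% | 3.4 | 5.2% |
| 2% | 9.5% | 6.8 | 11.7% |
| 3% | 10.5% | 10.2 | 22.0% |

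A normal approximation gives larger values (2.5% without bias; 6.7%, 14.3% and 25.8% at 1%, 2% and 3%). The Fisher figures are used because that is the planned test.

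If the planned effect is real, the inflation of the risk difference is (1 − 0.144) × e: 0.9, 1.7 and 2.6 percentage points at 1%, 2% and 3%, against a planned 6.7.

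**The case against.** **The overlap is inferred from a job title.** A reader might conclude that the same individuals recruit, deliver and assess. The protocol does not say so. A clinician gives the kit instructions in 3.4.1; the research team checks eligibility by telephone and online consent is electronic (3.6.3); a clinical studies officer meets participants on the paper pathway; delivery may fall to a CPN; and 3.8.2.1 plans to interview two MHR/CPNs per Trust. This stands. The point is that the protocol permits overlap and makes it likely, not that it prescribes it.

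**Section 3.5 does not declare researcher blinding impossible.** It says only that not all researchers can be blinded. This also stands. It leaves room to mask some of them, but the list of those blinded includes no one who collects outcomes.

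**Participants know their arm whoever telephones.** Much of any wish to please would survive a change of caller. This stands and limits what the fix can achieve. It does not bear on unequal probing or unequal effort to complete visits, which depend on the assessor.

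**CO verification is an objective check.** It limits false quits, and the assumed rates apply after CO, so raw over-claiming would have to be higher. But the self-report decides who is tested, and CO is a weaker filter for people who have cut down: 3.9 envisages CO falling from 18.5 to 13 ppm in reducers, so some continuing smokers may read below 10 ppm. CO reduction is also listed as an outcome for both arms (3.8.3.2, 4.5.2.1), which sits uneasily with testing only claimed abstainers. The postal option takes the caller out for some participants, though not the CO visit.

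**A caller from another Trust costs rapport and data access.** Retention is a progression criterion and loss counts as smoking, so this should be one option and not a requirement.

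**Conclusion.** The concern holds as a gap in safeguards. The protocol allows, and by its staffing makes likely, that an unblinded MHR who recruited a participant or delivered the kit also collects that participant's 1- and 6-month abstinence outcome. Nothing protects the telephone self-report that triggers CO testing, or the effort spent on completing CO visits.

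It would go too far to infer that assessor bias is present or that one person demonstrably does all three tasks. The documents give no size for the bias. The rise from 1.8% to 5.2%, 11.7% and 22.0% rests wholly on assumed rates of 1%, 2% and 3%, confined to the intervention arm and counted after CO. It charges all over-claiming to the caller, so at those rates it is an upper bound on what changing the caller could prevent; unequal CO effort is a separate route that it does not measure. What the range does show is that 3 to 10 people among 370 are enough to matter. No change in sample size follows. The change is worth making because it is cheap and the exposed outcome is the primary one.

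**What to change.** Amend 3.6.3, which 4.3 then carries into Phase II, to state that:

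- Follow-up is made by existing research staff who had no recruitment or delivery contact with that participant, where possible. An MHR of another Trust is one way to do this. Exceptions, such as Urdu calls where only one bilingual MHR is available, are recorded.
- Abstinence and cigarettes-per-day items are asked first, from a script, before any item that reveals the arm.
- The self-report is locked in REDCap before the CO visit.
- The same number of contact attempts and CO-visit attempts is made in both arms, and CO completion is reported by arm.

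In 3.5, state the masking status of the follow-up researchers. Reconcile 3.4.1 with 3.6.4 and 3.8.2.1 on who delivers the kit instructions.

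The cost is protocol wording, a call rota and a question order, without added staff. The downsides are some loss of rapport with a familiar caller and shared access to contact details if calls cross Trusts. Participant unblinding remains under any version of this change.

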3.8 Measures

3.8.1 Baseline measures

Baseline measures will be collected via a brief questionnaire and health records.

- *3.8.1.1 Socio-demographic characteristics:* These include age, sex, employment status, ethnicity, education, employment, accommodation type and marital status.
- 3.8.1.2 Smoking-related characteristics: These include general smoking characteristics, quit attempts and methods (including e-cigarettes), nicotine dependence [53], strength of urges to smoke (SUTS) [54], motivation to quit [55] and adexhaled breath carbon-monoxide (CO) reading.
- 3.8.1.3 General and mental health-related characteristics: These include most recent diagnosis (if available), antipsychotic medication use, and acute events (e.g. hospitalisation) in the last year. Mental health symptoms will be assessed with the PHQ-9 [56], GAD-7 [57] and SF-12 questionnaires [58].
- 3.8.1.4 Health behaviour characteristics: Alcohol use [59], exercise [60] and diet [61] will be assessed.

3.8.2 Primary outcome measures:

3.8.2.1 Feasibility and acceptability outcomes: The primary feasibility outcome measures in the feasibility trial will be consenting rate and recruitment frequency. Consenting rate will be calculated from the number of eligible participants approached who consent to take part in the study. The criterion to judge whether a large-scale RCT is feasible using the proposed recruitment approach is consenting a minimum of ~15% of eligible participants (see 3.14) which is slightly lower than the consenting rate typical in clinical trials in general patient populations in the UK [62]. Recruitment frequency will be calculated as the number of eligible patients at each site who agree to participate in the trial per month. Based on our projection of the number of participating trusts and sites in the full RCT, we would require around six participants per month from each Trust to deliver the full RCT successfully (see 3.9/4.4). MHR (or CPN) will be asked to record the number of non-eligible patients using a check list of common reasons for exclusions.

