3.8.3.1 Feasibility and acceptability outcomes: Fidelity will be assessed by randomly sampling two intervention sessions per site with trained staff, audio-recording them and coding the use of behaviour change techniques (BCTs) delivered during the session to determine the proportion of BCTs used compared to specification in the manual [66]. Characteristics of 'usual care' in different locations will be also noted, recording two interactions of patients with CMHTs or GPs at each site at baseline and using short proforma with control group participants at follow-up. While the nature of the intervention and delivery format means that contamination is unlikely to be a problem, qualitative exploration will be undertaken with 25% of control group patients to investigate in depth reasons for smoking behaviour change and identifying potential (unintentional) links with our intervention. Based on our findings, we will estimate the presence/extent of contamination in the control group, and the need to change the study procedure (e.g. spacing randomisation per site). Further, the feasibility of intervention delivery via CPNs and using both English and Urdu will be assessed by calculating the number of successfully trained CPNs in each Trust, their recruitment rate and fidelity of intervention delivery as well as the proportion of Urdu speakers successfully recruited into the trial. Participant burden of data collection will be asssessed via qualitative interviews conduction online or via telephone with particpants to assess acceptability, which forms part of our list of measures collected in the feasibility study (Phase 1) to determine stop/go decision for the Phase 2 full trial. Should this issue be raised as a barrier to participation, we will seek to prioritise which measures to retain in the full trial.

3.8.3.2 Clinical (smoking-related) outcomes: Self-reported abstinence 2-4 weeks from enrolment or target quit date (whichever is later) will be recorded at 1-month follow-up. The change in cigarette consumption (and reduction in exhaled breath CO reading) from baseline to 1-month follow-up will be calculated in both intervention and control group participants.

3.8.3.3 Clinical (mental health-related) outcomes: At 1-month follow-up, general and mental health functioning will be assessed as per baseline (see 3.8.1.3).

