3.9 Power Calculation

The target sample size for the randomised controlled feasibility trial will be 72, with 36 participants allocated to each group. In a full RCT, we would assume an effect size of OR (odds ratio) of 3.9 (pooled estimate based on e-cigarette vs placebo e-cigarette trials: [38, 39]) for the primary clinical outcome (1-month continuous abstinence rate). This would result in an absolute predicted risk difference of 8.2%, assuming a 1-month abstinence rate in the control (usual care) group of 11.4% [based on EAGLES trial [67]] and 19.6% in the intervention (e-cigarette starter kit and usual care) group. The pilot sample size would be sufficient to produce a one-sided confidence interval that excludes an 8% difference in the event of a zero effect of the intervention on abstinence at 1 month, assuming 11% reported abstinence in each of the two groups. The estimate obtained in the feasibility trial will not be used to directly estimate the intervention effect (see 2.5) but to determine whether proceeding to a trial is worthwhile, based on the confidence interval approach [47].

In addition, the Phase I study is powered to detect clinically relevant within-subject changes in two secondary clinical outcome measures: cigarette and exhaled breath CO reductions. A recent study [8] in which smokers with mental illness, who were not intending to quit smoking, were provided with e-cigarettes showed that half of smokers

reduced their cigarette consumption by 50%. This e-cigarette supported level of reduction has been linked to a significant lowering in exposure to biomarkers of smoking-related harm [68]. Further, such smoking reduction in concert with provision of non-combustible nicotine delivery devices may aid future complete cessation [69]. The target outcome is therefore a reduction in cigarette consumption by at least 50% (or a 30% reduction in CO levels, common for smoking reduction of this magnitude [70]). Half the sample size in the intervention group (those expected to reduce consumption, n=18) provides 80% power to detect a medium- to large-sized effect (Cohen's d=0.7), reflecting a 50% reduction in cigarettes smoked per day from 12 to 6 cigarettes (average cigarette consumption based on population samples (e.g. [71]) and a 30% reduction in CO levels (from 18.5 to 13 parts per million (ppm); baseline estimate based on a opportunistically recruited population sample [72]).

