4.5.2 Secondary outcome measures

- 4.5.2.1 Clinical (smoking-related) outcomes: At one month, self-reported and CO-verified smoking abstinence rates, 2-4 weeks from enrolment or target quit date (whichever is later) will be recorded. Continuous abstinence at 6-month follow-up will be defined as not having had more than 5 cigarettes between two weeks after enrolment and follow-up, in line with Russell standards [77]. Unsuccessful quit attempts in the past six months will also be recorded. In line with the feasibility trial, smoking reduction in cigarette consumption by 50% or in CO reading by 30% will be assessed at both 1- and 6-month follow-up.
- 4.5.2.2 Clinical (mental health-related) outcomes: At 6-month follow-up only, general and mental health functioning will be assessed using measures detailed in 3.8.1.3.
- 4.5.2.3 Practical (design-related) outcomes: As in Phase I, attrition and, in the intervention group, adherence rate will be assessed at 1-month follow-up. Attrition will also be assessed at 6-months follow-up, in addition to continued use of e-cigarettes in the intervention group and de novo e-cigarettes use in the control group.
- 4.5.2.4 Psychosocial outcomes: Health-related quality of life will be assessed using EQ-5D-5L [82] and the mental health specific ReQoL [83] at final follow-up. Health and social care service use will be measured using the Client Service Receipt Inventory (CSRI), which has been validated against objective primary care records [84] and is also recommended for usage of hospital and other community health services [85]. Changes from baseline in other health behaviours (see 3.8.1.4) will be determined at 6-month follow-up.
- 4.5.2.5 Cost effectiveness: To determine short-term cost-effectiveness of the intervention, we will undertake a within-trial incremental cost-effectiveness analysis to assess the value

for money afforded by the intervention over and above the usual care using data collected during the trial. A service use questionnaire piloted in the feasibility workstream will be used to collect resource use at baseline, one and six months and will include both the cost of providing the interventions and the costs of patients' health care utilisation from an NHS perspective as recommended by NICE technology appraisal guide [86]. To assess long-term cost, effectiveness, we will undertake economic modelling (see 4.7).

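### Section 3.6.3 plans follow-up CO readings for self-reported abstainers only, which contradicts the CO-reduction outcomes in both arms and the CO power claim in 3.9

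*Protocol*

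**What the plan says.** **Follow-up procedure (Protocol 3.6.3).** "Follow-up surveys will be completed via telephone with an option to receive this by post if preferred". An in-person visit "will be required to biochemically validate self-reported abstinence only through carbon monoxide readings", and the same sentence sizes this workload as "likely to affect approximately 12 participants in phase 1, and 94 participants in phase 2", tying both counts to expected abstinence. Section 4.3 carries the procedures into Phase II, subject to what Phase I teaches.

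**CO reduction as an outcome.**
- 3.8.3.2 (Phase I) names a CO outcome next to the number of cigarettes smoked: "and reduction in exhaled breath CO reading) from baseline to 1-month follow-up will be calculated in both intervention and control group participants".
- 3.10 analyses CO readings in a generalised linear model with allocation as the between-group factor and time as the within-group factor.
- 4.5.2.1 (Phase II) states that "smoking reduction in cigarette consumption by 50% or in CO reading by 30% will be assessed at both 1- and 6-month follow-up".
- 3.9 claims 80% power in 18 intervention-arm reducers for a standardised effect of 0.7, said to reflect "a 30% reduction in CO levels (from 18.5 to 13 parts per million".

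**Baseline.** 3.8.1.2 lists an exhaled CO reading among the baseline measures, but 3.8.1 opens with "Baseline measures will be collected via a brief questionnaire and health records". Under 3.6.3, online-pathway participants complete the baseline in REDCap and then learn their allocation. Under 3.4.1 their clinical appointment may itself be online. The study flow chart, by contrast, shows an on-site baseline assessment. Its footnote, which appears to concern follow-up, places assessment at clinics or the participant's home and does not limit it to abstainers.

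**The concern.** A person who cuts down but still smokes, and says so on the telephone, has no follow-up CO reading under 3.6.3. That is the person whom the CO-reduction outcome and the CO power statement are about. Harm reduction is part of the trial's main aim (section 2), and CO is the only objective measure of reduction in the plan.

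If 3.6.3 is followed, the CO comparison between arms is made in the people who report abstinence. That group is defined after randomisation, and its size is expected to differ by arm because the intervention is meant to increase it. The comparison would then lack the protection of randomisation, besides being small. Progression criterion (d) in 3.13 also looks at the proportion of participants from whom CO was obtained, and the contradiction leaves the denominator of that proportion unclear.

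**Working it through.** **1. Are the visit counts in 3.6.3 counts of abstainers?** Expected abstainers = number per arm × (control rate + intervention rate).
- Phase I, rates from 3.9: 36 × (0.114 + 0.196) = 36 × 0.310 = 11.2, against a stated 12.
- Phase II, rates from 4.6: 370 × (0.077 + 0.144) = 81.8 with the conservative effect, or 370 × (0.077 + 0.169) = 91.0 with the effect called more likely, against a stated 94.

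The Phase I figure reproduces to within one participant. The Phase II figure does not reproduce exactly; the nearest value is 3 lower. Both are of the size of an abstainer count and far from the full sample, so visits are planned for abstainers only.

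**2. Share of participants with a follow-up CO reading.**
- Phase I: 12/72 = 16.7%, leaving 72 − 12 = 60 without one.
- Phase II: 94/740 = 12.7%, leaving 740 − 94 = 646 without one.
- Phase II at 1 month, if the 1-month rates in 3.9 applied: 370 × 0.310 = 114.7, and 114.7/740 = 15.5%.

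**3. The power claim in 3.9.** Inputs: n = 18, d = 0.7. Alpha and sidedness are not stated for this calculation; I assume a two-sided paired t-test at 5%. The noncentrality parameter is 0.7 × √18 = 2.97 on 17 degrees of freedom, and power is 79.9%. The stated 80% reproduces. (A one-sided test would give 88.6%.)

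**4. Whom that claim describes.** The fall from 18.5 to 13 ppm is 1 − 13/18.5 = 29.7%. The end value of 13 ppm lies above the 10 ppm limit for verified abstinence (3.8.2.2, 4.5.1). The assumed responder is therefore not a verified abstainer, and under 3.6.3 has no reading unless he or she reports abstinence.

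**5. Readings expected under 3.6.3.** Intervention arm: 36 × 0.196 = 7.1, about 7. Control arm: 36 × 0.114 = 4.1, about 4. If the 7 could stand in for the 18, the noncentrality parameter would be 0.7 × √7 = 1.85 on 6 degrees of freedom, and power 34.5%. With 8 readings it would be 40.1%. This substitution is generous to the plan, because the 7 are self-reported abstainers and not the reducers for whom the effect was assumed.

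**6. Baseline.** A change or a percentage fall also needs a baseline reading. The paper pathway includes a face-to-face meeting before allocation at which one could be taken. For the online pathway the order is remote baseline, allocation, then an appointment that may be remote. No CO reading before randomisation is described.

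**The case against.** The strongest reply is that the protocol does contain text under which CO could be collected from everyone: the flow chart has an on-site baseline and a footnote that does not restrict clinic or home assessment to abstainers, and 3.8.1.2 lists CO as a baseline measure. This stands in part. It means the plan contradicts itself, and a reader who infers that CO reduction cannot be measured at all goes further than the documents allow. It does not settle the matter for universal collection, because 3.6.3 is the more detailed procedure and the only one with visit numbers attached.

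Other stronger readings are tempting and not supported:
- *That at least 83% to 87% would have no follow-up CO.* The counts come from expected abstinence, and the primary outcomes behind those rates are CO-verified. Self-reported abstainers should be at least as many, so these percentages are approximate and nearer an upper figure.
- *That a continuing smoker can never meet the CO limb.* Someone who reports abstinence but reads 10 ppm or more is measured, and a fall from 18.5 to 12 ppm would qualify.
- *That the CO limb merely repeats abstinence.* A reading below 10 ppm guarantees a 30% fall only from a baseline of about 10/0.7 = 14.3 ppm or more, and the protocol gives no baseline distribution.
- *That unmeasured reducers are coded as failures.* The rule in 4.7.1 that treats people as smokers covers those lost to follow-up. A reducer reached by telephone is not lost, so the handling of the missing reading is open.
- *That the online pathway has no visit.* The appointment may be in person. The narrower statement holds: no CO reading before randomisation is described for it.

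It is also fair to say that 3.13 and 4.3 allow procedures to be amended after Phase I. That helps Phase II but not the Phase I outcome or its power claim.

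**Conclusion.** The contradiction holds and should be fixed. Following 3.6.3 gives follow-up CO in roughly 17% of Phase I and 13% of Phase II participants, selected by smoking status after randomisation, and leaves the CO half of the power statement in 3.9 largely without the data it needs: about 7 intervention-arm readings, and about 35% power even on a generous substitution. These sizes rest on the protocol's own abstinence rates and visit counts, and on a two-sided 5% paired test for the power figure.

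The reach is limited. CO reduction is a secondary outcome in both phases. The abstinence outcomes do not depend on it, and the 50% cigarette limb can be collected by telephone from everyone, with its own power statement intact. A reader might infer that the trial could then say nothing about harm reduction; that would be true of the CO limb only.

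**What to change.** Reconcile the flow chart with 3.6.3, 3.8.1, 3.8.3.2, 3.9, 3.10 and 4.5.2.1, in one of two ways.

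**If 3.6.3 stands:** withdraw the CO part of the power claim in 3.9. Drop the CO-change comparison from 3.8.3.2 and 3.10 and the CO limb from the reduction outcome in 4.5.2.1. Define reduction as a fall of at least 50% in self-reported cigarettes per day. Show any CO change descriptively, labelled as coming from self-reported abstainers with a baseline reading. State how and when baseline CO is taken on each pathway, or that it is not taken on the online one. The cost is wording only, with no added visits. The price is that reduction then rests on self-report alone, in a trial whose participants know their allocation (3.5).

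**If CO reduction is to be kept as an outcome:** state that CO is measured at baseline, before allocation, and at each follow-up in every participant on both pathways. This keeps an objective measure, but needs follow-up visits for about 60 more participants in Phase I and 646 more in Phase II (at 1 and 6 months if 4.5.2.1 is kept), plus a baseline visit for the online pathway.

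Under either choice, give the denominator for the CO-collection proportion in criterion (d) of 3.13.
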